During regorafenib treatment:

- Avoid pressure points
- Avoid items that rub, pinch or create friction

Use of creams

Apply non-urea based creams liberally, e.g.,

- Cetaphil
- Aveeno
- Udderly Smooth
- Gold Bond
- Norwegian Formula
- Eucerin

Keratolytic Creams: Use sparingly and only to affected (hyperkeratotic) areas

- Urea-based creams
- Salicylic acid 6%

Alpha Hydroxy Acids (AHA) based creams

- Approximately 5-8% provide gentle chemical exfoliation
- Apply liberally two times each day

Topical analgesics like lidocaine 2% to be considered for pain control (114)

Topical corticosteroids like clobetasol 0.05% should be considered for subjects with Grade 2 or 3 hand-foot skin reaction (114). Avoid systemic steroids.

Cushions

Protect tender areas

- Use socks/gloves to cover moisturizing creams
- Wear well-padded footwear
- Use insole cushions or inserts (e.g., silicon, gel)
- Foot soaks with tepid water and Epsom salts

Table 12: Management of treatment-emergent hypertension

NCI- CTCAE	Definition	Antihypertensive therapy	Regorafenib dosing
V5.0 grade	Prehypertension (systolic BP 120 - 139 mmHg or diastolic BP 80 - 89 mmHg)	None	Continue regorafenib. Consider increased BP monitoring.
2	Systolic BP 140 - 159 mmHg or diastolic BP 90 - 99 mmHg,	Treat with the aim to achieve diastolic BP ≤ 90 mmHg:	Continue regorafenib.
	OR Symptomatic increase by > 20 mmHg (diastolic) if previously within normal limits	 If BP previously within normal limits, start antihypertensive monotherapy. If subject already on antihypertensive medication, titrate up the dose. 	If symptomatic, hold regorafenib until symptoms resolve AND diastolic BP ≤ 90 mmHg. ^a When regorafenib is restarted, continue at the same dose level.

3	Systolic BP ≥ 160 mmHg or diastolic BP ≥ 100 mmHg OR More than one drug or more intensive therapy than previously used indicated	Treat with the aim to achieve diastolic BP ≤ 90 mmHg: - Start antihypertensive medication AND/OR - Increase current antihypertensive medication AND/OR - Add additional Antihypertensive medications.	Hold regorafenib until diastolic BP ≤ 90 mm Hg, and if symptomatic, until symptoms resolve. ^a When regorafenib is restarted, continue at the same dose level. If BP is not controlled with the addition of new or more intensive therapy, reduce by 1 dose level. be If Grade 3 hypertension recurs despite dose reduction and antihypertensive therapy, reduce another dose level. ce
4	Life-threatening consequences (e.g, malignant hypertension, transient or permanent neurologic deficit, hypertensive crisis		Discontinue therapy

BP = blood pressure; NCI-CTCAE=National Cancer Institute-common terminology criteria for adverse events a Subjects requiring a delay of study treatment > 4 weeks should go off regorafenib.

Blood Pressure should be monitored weekly for the first 6 weeks of treatment. The blood pressure will be recorded by the treating physician and entered onto the e-CRF.

Any blood pressure that is out of normal range must be reported to the treating physician. Blood pressure measurements considered out of normal range are diastolic \geq 100 mmHg and systolic \geq 150 mmHg, or a \geq 20 mmHg increase in diastolic measurement if the measurement was previously within normal limits.

b If BP remains controlled for at least one full cycle, dose re-escalation is permitted at the investigator's discretion.

c Subjects requiring > 2 dose level reductions (< 80 mg reduction) should go off regorafenib therapy.

d Cf table a.

The dose modification schedule for treatment emergent hypertension during regorafenib dosing should be followed (see [Table 12]). Subjects' blood pressure (BP) measurements will be monitored and appropriate treatment to effectively control hypertension under regorafenib treatment is strongly recommended.

The selection of anti-hypertensive medication used in this setting should be performed at the investigator's discretion, considering possible site-specific treatment guidelines. All medication should be recorded in the subjects e-CRF.

Table 13: Drug-related liver dysfunction

Elevations of	Occurence	Management
alanine aminotransférase (ALT)		
and/or aspartate aminotransférase (AST)		
≤ 5 times upper limit of normal (ULN) (Grade	Any	Continue treatment by
2)	occurence	Regorafenib. Control liver
		function every week until ALT
		and AST values resolve to < 3
		times ULN (grade 1) or to
		their initial value.
> 5 times ULN AND ≤ 20 times ULN (Grade 3)	1st occurence	Interrupt Regorafenib.
		Control ALT and AST
		values every week until
		they resolve to < 3 times
		ULN or their initial value.
		Resuming treatment: if the
		benefice is superior to the
		risk of hepatic toxicity,
		reintroduce Regorafenib
		and reduce the dose of
		one tablet (40 mg) and
		control liver function every
		week for at least 4 weeks.
	2 nd	Discontinue regorafenib
	occurence	permanently

> 20 times ULN (Grade 4)	Any	Discontinue regorafenib
	occurence	permanently
> 3 times ULN (Grade 2 or beyond) with	Any	Discontinue regorafenib
concomitant elevation of bilirubin > 2 times	occurence	permanently
ULN		
		Interrupt Regorafenib until
		toxicity resolves to Grade 0-1.
		Control liver function every
		week until ALT and AST
		values resolve to < 3 times
		ULN (grade 1) or to their
		initial value.

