6.3 Dose modification and Dose delay

ARM A: REGIRI

Regorafenib: Dosage changes should be made in 40 mg increments (1 tablet). The recommended daily dose of Regorafenib is 160 mg.

Dose reductions of Regorafenib	
1 st reduction: 120 mg	
2 nd reduction: 80 mg	

Table a*

Digestive toxicity: Diarrhea

A symptomatic treatment of the diarrhea occurring more than 24 hours after the irinotecan administration is possible by diosmectite (Smecta®), 1 sachet/8h and loperamide (Imodium®), 2 capsules/8h until 24 hours after the last stool which is loose or watery. If, in spite of this treatment, the diarrhea is not under control in the first 24 hours then fluoroquinolones as antibiotics will be orally given during 7 days.

In case of diarrhea > grade 1, the patient will receive during the next courses of treatment a prophylactic treatment by sucralfate (Keal®) 1 sachet / 6 h et Ercefuryl® 200 at a rate of 3 capsules/24 h.

Table 1: Action and dose modification during the administration of Irinotecan and Regorafenib after the first course of treatment in case of diarrhea

Protocole NEXT-REGIRI -Version 6.0 du 09/11/2023

Page **41** sur **86**

Grade	During the course of treatment	dose at the next course of treatment
Grade 1	NA	Irinotecan at 150 mg/m². Regorafenib at 160 mg per day + prophylactic treatment
Grade 2	Interrupt irinotecan until diarrhea resolves to Grade ≤ 1	Irinotecan at 120 mg/m². Regorafenib at 160 mg per day + prophylactic treatment
Grade 3	Interrupt irinotecan until diarrhea resolves to Grade ≤ 1	Irinotecan at 120 mg/m² and Regorafenib at 120 mg per day
Grade 4	Discontinue treatment permanently	Discontinue treatment permanently

Table 2: Action and dose modification during the administration of Irinotecan and Regorafenib after the second course in case of diarrhea

Grade	During the course of	Dose at the third course of	
Grade	treatment	treatment	
		Dose-escalation of irinotecan is	
Grade 1	NA	permitted. Regorafenib at 160	
Grade I	INA	mg per day	
		+ prophylactic treatment	
		Dose-escalation of irinotecan is	
Condo 2	Interrupt irinotecan until diarrhea resolves to Grade	not permitted. Regorafenib at	
Grade 2	≤ 1	160 mg per day	
		+ prophylactic treatment	
	1st accurrance: Interrupt	1st occurrence: Decrease	
Grade 3	1st occurrence: Interrupt irinotecan until diarrhea	Irinotecan to 120 mg/m².	
	resolves to Grade ≤ 1	Regorafenib to 160 mg per day	

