	2 nd occurrence: Interrupt irinotecan until diarrhea resolves to Grade ≤ 1	2 nd occurrence: Irinotecan dose is not changed at 120 mg/m² and decrease Regorafenib to 120 mg per day
	3rd occurence : Discontinue treatment permanently	3rd occurence : Discontinue treatment permanently
Grade 4	Discontinue treatment permanently	Discontinue treatment permanently

Table 3: Action and dose modification during the administration of Irinotecan and Regorafenib after the third course and beyond in case of diarrhea

	Grade	During the course of treatment	Dose at the third course of treatment
Grade 1-2		Interrupt irinotecan until diarrhea resolves to Grade ≤ 1	No dose modification + prophylactic treatment
Grade 3	Patients having	 1st occurrence: Interrupt irinotecan until diarrhea resolves to Grade ≤ 1 2nd occurrence: Interrupt irinotecan until diarrhea resolves to Grade ≤ 1 	1st occurrence: Decrease Irinotecan to 150 mg/m². Regorafenib to 160 mg per day 2nd occurrence: Decrease Irinotecan to 120 mg/m². Regorafenib to 160 mg per day
	received the irinotecan dose of 180 mg/m2	3 rd occurence : Interrupt irinotecan until diarrhea resolves to Grade ≤ 1	3 rd occurrence: Irinotecan is not changed at 120 mg/m² and decrease Regorafenib to 120 mg per day

		4th occurence : Discontinue treatment permanently	4th occurrence: Discontinue treatment permanently
		1 st occurrence: Interrupt irinotecan until diarrhea resolves to Grade ≤ 1	1st occurrence: Decrease Irinotecan to 120 mg/m². Regorafenib to 160 mg per day
	Patients having received the irinotecan dose of 150 mg/m²	2 nd occurrence: Interrupt irinotecan until diarrhea resolves to Grade ≤ 1	2 nd occurrence: Irinotecan is not changed at 120 mg/m² and decrease Regorafenib to 120 mg per day
	3rd occurence : Discontinue treatment permanently	3rd occurence : Discontinue treatment permanently	
	Patients having received the irinotecan dose of 120 mg/m²	1st occurrence: Interrupt irinotecan until diarrhea resolves to Grade ≤ 1	1st occurrence: Irinotecan is not changed at 120 mg/m² and decrease Regorafenib to 120 mg per day
		2nd occurrence: Discontinue treatment permanently	2nd occurrence: Discontinue treatment permanently
Grade 4		Discontinue treatment permanently	Discontinue treatment permanently

Hematologic toxicity

Table 4: Action and dose modification during the administration of Irinotecan in case of hematologic toxicity

CBC at D15	Delayed Treatment	Decrease the dose for the next courses of treatment

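### Section 6.3 (arm A) gives inconsistent triggers for diarrhoea prophylaxis: the text sets it above grade 1, while Tables 1-3 list it at grades 1 and 2 and in no grade 3 row

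*Combined protocol and SAP*

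**What the plan says.** Section 6.3 of the combined protocol and SAP governs dose changes. Its arm A part opens the diarrhoea rules with text on symptomatic treatment, followed by a general rule for later courses: "In case of diarrhea > grade 1, the patient will receive during the next courses of treatment a prophylactic treatment". The agents are then named. The sentence is mandatory and carries no exception.

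Three tables follow, for diarrhoea after the first course, after the second, and after the third and beyond. Their last column gives the doses at the following course and, in some rows, adds prophylaxis:

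- **Table 1.** Grade 1: "Irinotecan at 150 mg/m². Regorafenib at 160 mg per day + prophylactic treatment". Grade 2: "Irinotecan at 120 mg/m². Regorafenib at 160 mg per day + prophylactic treatment". Grade 3: "Irinotecan at 120 mg/m² and Regorafenib at 120 mg per day", with no mention of prophylaxis.
- **Table 2.** The grade 1 and grade 2 rows both carry "prophylactic treatment". At grade 3, the first occurrence lowers irinotecan and ends with "Regorafenib to 160 mg per day"; the second reads "Irinotecan dose is not changed at 120 mg/m² and decrease Regorafenib to 120 mg per day". Neither mentions prophylaxis.
- **Table 3.** Grades 1 and 2 share one row: "No dose modification + prophylactic treatment". The grade 3 entries, split by irinotecan dose received and by occurrence, give doses only.

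Grade 4 means permanent discontinuation in all three tables.

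**The concern.** The text and the tables should express one rule. Read on its own, the text starts prophylaxis at grade 2 and carries it into grade 3. Read on their own, the tables start it at grade 1 and do not show it at grade 3.

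Because the tables add prophylaxis in some rows, a site using them as its working reference could reasonably take its absence at grade 3 as intended. A site following the sentence would give it at grade 3 and would have no instruction to give it at grade 1. The trial is open and multicentre, so such differences would fall between sites within arm A. What is at stake is consistent conduct of a stated safety rule, above all after grade 3, the most severe grade after which treatment can continue.

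**Working it through.** No formula applies, because the point depends on no sample size, event count, power or alpha. The check sets the sentence against each table row by grade.

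| Grade | Text, section 6.3 | Table 1 | Table 2 | Table 3 | Result |
|---|---|---|---|---|---|
| 1 | Below the trigger; not mentioned | Listed | Listed | Listed (merged row) | Mismatch by implication |
| 2 | Required | Listed | Listed | Listed (merged row) | Agree |
| 3, treatment continuing | Required | Not listed | Not listed | Not listed | Mismatch by omission |
| 4 | Does not arise | Treatment stops | Treatment stops | Treatment stops | Not applicable |

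**Count of grade 3 entries after which treatment continues.**
- Table 1: 1.
- Table 2: 2 (first and second occurrence; the third stops treatment).
- Table 3: 3 for patients who had received 180 mg/m², 2 for 150 mg/m² and 1 for 120 mg/m², so 3 + 2 + 1 = 6.
- Total: 1 + 2 + 6 = 9. Prophylaxis is listed in 0 of the 9.

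**Count of grade 1 and grade 2 rows.** Two in Table 1, two in Table 2 and one merged row in Table 3: 2 + 2 + 1 = 5. Prophylaxis is listed in 5 of 5.

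**Could the sign in the text be a misread character?** If it meant grade 1 or above, the grade 1 mismatch would vanish and the grade 3 mismatch would remain. The documents give no sign of a misreading: section 6.1 uses the same above-grade-1 threshold for diarrhoea in the irinotecan escalation rule.

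**Could it be a fault of text extraction?** Table 2 is broken in the extracted text but can be read. Tables 1 and 3 are clear, and all three show the same pattern.

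**Do the dose rules conflict as well?** On escalation they do not. Section 6.1 withholds it for diarrhoea above grade 1. Tables 1 and 2 let irinotecan rise after grade 1 and not after grade 2.

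**The case against.** The strongest reply is that a site can obey every passage at once. The sentence sits directly above the tables, is mandatory and has no exception, so it still applies at grade 3. The last column of each table is headed as a dose column, and its silence on supportive medication forbids nothing. At grade 1 the sentence sets a trigger for higher grades and says nothing about that grade, so the tables merely add to it. Read together, the passages give prophylaxis at grades 1 to 3.

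Much of this stands. A reader might infer that text and tables give opposite instructions; they do not, since nothing in either prohibits what the other gives. A reader might also infer that patients with grade 3 diarrhoea get no prophylaxis under the plan; that happens only if a site overlooks the sentence.

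The merged row for grades 1 and 2 in Table 3 can look like a further contradiction, because it interrupts irinotecan until diarrhoea is grade 1 or lower, while Tables 1 and 2 call for no action at grade 1. At grade 1 the condition is already met, so the outcome is the same.

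The reply does not make the wording consistent. If the sentence were meant to govern every row, the note would be redundant at grade 2. Printing it there, extending it to grade 1 and leaving it out at grade 3 invites the reading that the tables are complete in themselves. The combined reading is possible, but the protocol does not state it.

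**Conclusion.** The inconsistency is real and limited. Text and tables match at one of the three grades at which treatment can continue. Grade 1 differs by implication and grade 3 by omission. The practical risk is that sites manage the same grade differently, and that a site relying on the tables alone leaves out prophylaxis that the text requires after grade 3. This assumes that some sites will work from the tables without the sentence; the documents do not show how often.

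Two larger claims are not supported. First, a reader might infer that arm A dose intensity depends on which passage is followed. Neither reading of the prophylaxis rule alters a dose, escalation, interruption or stopping rule. Any effect would be indirect, through later diarrhoea, and the documents give no figure for it.

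Second, a reader might size the problem from the diarrhoea rates in the background section: 60% of any grade with regorafenib plus FOLFIRI in the phase Ib trial, and 14% of grade 3 or higher in the randomised phase II. Those regimens contain 5-FU and differ from REGIRI. The 60% includes grade 2, where text and tables agree, and the 14% includes any grade 4, at which this protocol stops treatment. Neither rate counts patients in the mismatched grades.

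No endpoint, sample size, analysis population or test is affected.

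**What to change.** The sponsor should reconcile the sentence in section 6.3 with Tables 1-3. One statement should name the diarrhoea grades that trigger prophylaxis at later courses, and every row after which treatment continues, including each grade 3 entry, should agree with it. The sponsor must say which rule is intended; this review proposes none. The merged row for grades 1 and 2 in Table 3 can be tidied at the same time, because its interruption instruction has no effect at grade 1.

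The cost is a wording amendment and notice to sites. Because the passage is a safety rule, the sponsor should decide under section 12.6 whether the change counts as substantial. No analysis or sample-size text needs to change.

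### Arm A diarrhoea Tables 2 and 3 state regorafenib 160 mg without regard to the current dose, so read literally they undo an earlier reduction; Table 2 also leaves a patient on irinotecan 120 mg/m² and regorafenib 160 mg unreduced after a first grade 3

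*Combined protocol and SAP*

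**What the plan says.** Doses are written irinotecan mg/m² / regorafenib mg per day.

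Section 6.1 starts arm A at 120/160. Irinotecan rises to 150 and then 180 mg/m² provided that diarrhoea has not exceeded grade 1 and other toxicity has not exceeded grade 2. Table a in section 6.3 gives two reduced regorafenib levels, 120 and 80 mg. Three tables then set the dose after diarrhoea.

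- **Table 1 (after course 1).** Grade 2: "Irinotecan at 120 mg/m². Regorafenib at 160 mg per day + prophylactic treatment". Grade 3: "Irinotecan at 120 mg/m² and Regorafenib at 120 mg per day".
- **Table 2 (after course 2).** The title, "Irinotecan and Regorafenib after the second course in case of diarrhea", sets no condition on the dose received. Grade 1 allows irinotecan to rise and continues "permitted. Regorafenib at 160" mg. Under grade 2, irinotecan escalation is "not permitted. Regorafenib at" 160 mg. A first grade 3 takes irinotecan to 120 mg/m² and "Regorafenib to 160 mg per day". A second grade 3 reads "Irinotecan dose is not changed at 120 mg/m² and decrease Regorafenib to 120 mg per day".
- **Table 3 (course 3 onward).** Grades 1 and 2: "No dose modification + prophylactic treatment". Grade 3 is split by irinotecan dose. The cells for 180 mg/m² (first and second occurrence) and 150 mg/m² (first occurrence) state 160 mg. The remaining cells go to 120 mg or stop treatment.

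In arm A regorafenib can also be cut for haematological toxicity (Table 5), other non-haematological toxicity (Table 6, which leaves diarrhoea out), hand-foot reaction (Table 7), hypertension (Table 8) and transaminase rises (Table 9). Only Tables 7 and 8 carry a re-escalation note for this arm.

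**The concern.** A dose-modification table should never raise a drug because a toxicity occurred. Table 2 and part of Table 3 give absolute regorafenib doses that suit a patient still on 160 mg. They do not say what to do with a patient whom another row or table has already reduced. An investigator who follows the cell as printed puts that patient back on the standard dose straight after an episode of diarrhoea. In one Table 2 situation, a first grade 3 episode reduces neither drug, although the neighbouring tables reduce regorafenib for the same event at the same dose.

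What is at stake is the next regorafenib dose of individual arm A patients. Section 11.2 has monitors check that the protocol is followed accurately, so an investigator who sensibly keeps the lower dose departs from the printed cell.

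**Working it through.** The plan gives no figure to reproduce. The check applies each cell literally to a current regorafenib dose and takes the new dose minus the current dose.

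**Step 1: cells that state a regorafenib dose.** Discontinuation rows and Table 3's grade 1-2 row are left out.

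| Cell | Regorafenib stated | From 160 mg | From 120 mg |
|---|---|---|---|
| Table 2, grade 1 | 160 | 0 | +40 |
| Table 2, grade 2 | 160 | 0 | +40 |
| Table 2, grade 3, 1st | 160 | 0 | +40 |
| Table 2, grade 3, 2nd | 120 | -40 | 0 |
| Table 3, 180 mg/m², 1st | 160 | 0 | +40 |
| Table 3, 180 mg/m², 2nd | 160 | 0 | +40 |
| Table 3, 180 mg/m², 3rd | 120 | -40 | 0 |
| Table 3, 150 mg/m², 1st | 160 | 0 | +40 |
| Table 3, 150 mg/m², 2nd | 120 | -40 | 0 |
| Table 3, 120 mg/m², 1st | 120 | -40 | 0 |

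Three of four cells in Table 2 and three of six in Table 3 fix 160 mg. From 120 mg the rise is 40/120 = 33%. From 80 mg, which needs two earlier reductions and is rarer, the 160 mg cells give +80 mg (80/80 = 100%). The cells worded as a decrease to 120 mg give +40 mg (40/80 = 50%).

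**Step 2: routes to a rise.**

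- *Diarrhoea alone.* Grade 3 in course 1 gives 120/120 (Table 1). Grade 1 or 2 in course 2 then gives regorafenib 160 mg (Table 2). No counting of occurrences is involved.
- *Another toxicity, then a first grade 3 diarrhoea.* Grade 3 haematological toxicity in course 1 cuts regorafenib to 120 mg (Table 5) and fails the section 6.1 condition for 150 mg/m². The patient is therefore taken to enter course 2 on 120/120. A first grade 3 diarrhoea gives 120/160 under Table 2: irinotecan unchanged, regorafenib up 40 mg. This is a first occurrence under any counting rule.
- *Same pattern in Table 3.* From 150/120, a first grade 3 gives 120/160. From 180/120, it gives 150/160.

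**Step 3: first grade 3 at 120/160.** Grade 2 in course 1 leaves the patient on 120/160 (Table 1).

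- Table 2, first grade 3: 120/160, so 0% change in both drugs.
- Table 1, grade 3 from the starting 120/160: 120/120.
- Table 3, 120 mg/m² row, first grade 3: 120/120.

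The last two cut regorafenib by 40/160 = 25%. Table 2 is the outlier.

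**Step 4: Table 2, second occurrence.** Take a patient on 120/120 after a course 1 grade 3 who has another after course 2. If occurrences are counted from course 1, this row applies and the dose stays 120/120. If the count restarts, the first-occurrence row applies and regorafenib goes to 160 mg. Neither gives a reduction, and the protocol does not say which count holds.

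**The case against.** The strongest reply is that 160 mg is shorthand for no change, and that a standing reduction should survive. There is support for this. Table a numbers its reductions, and the notes to Tables 5, 6 and 7 stop treatment when more than two are needed, so reductions accumulate. Tables 7 and 8 grant re-escalation expressly, which suggests that it is not the default elsewhere. This is probably what the authors meant, and the literal rise is not the only reading. But no arm A text says that the earlier reduction prevails. Where these tables intend no change they can say so, as Table 3's grade 1-2 row does. The reply also leaves the 120/160 cell untouched.

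Other points limit the concern:

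- Table 2's second-occurrence row presupposes a patient already on irinotecan 120 mg/m², which favours counting from course 1. On that count, a rise after a first grade 3 needs an earlier cut for another toxicity, which is a narrower sequence.
- Arm B's Table 10 allows discretionary re-escalation after a grade 3, so a return to 160 mg is not foreign to this protocol.
- There are safeguards. Irinotecan is held until diarrhoea is grade 1 or lower, prophylaxis follows diarrhoea above grade 1, and grade 4 stops treatment. Arm A has contacts on days 8, 15 and 22 of cycles 1 and 2. Investigators may stop treatment (section 8.1), and the safety committee reviews the first twenty arm A patients (section 10.3). None of these sets the next regorafenib dose.
- The extracted text of Table 2 is imperfect, and Table a carries an asterisk whose note is not visible. A clarifying note there cannot be wholly excluded.

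A reader might infer that Table 2 works only for a patient on 150/160. It does not go that far: the grade 1 and 2 rows name no irinotecan dose and fit 120/160 equally well. Nor does Table 3 leave grade 3 diarrhoea at 120 mg/m² without limit, because a second occurrence there stops treatment.

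**Conclusion.** The concern holds as a defect in the written dosing rule. Six of the ten cells in Tables 2 and 3 that state a regorafenib dose fix it at 160 mg. Read literally, they add 40 mg (33%) for a patient on 120 mg, back to the standard dose and never above it. Table 2 also gives no reduction for a first grade 3 at 120/160, against a 25% regorafenib cut under Tables 1 and 3, and none in its second-occurrence row for a patient already on 120/120.

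The rise rests on the literal reading and on the absence of any arm A text giving priority to an earlier reduction. The 120/160 inconsistency needs neither assumption. The number of patients affected cannot be derived from the documents and is probably small.

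Two stronger inferences are not supported. One is that patients will in fact be re-escalated: the likely intent and clinical judgement both point the other way. The other is that the overall survival comparison is biased: nothing in the documents shows that, and it is not claimed.

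**What to change.** Amend section 6.3, arm A:

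1. In Tables 2 and 3, replace each fixed regorafenib 160 mg with the current regorafenib dose, adding that it is not re-escalated except as Tables 7 and 8 allow.
2. In the same tables, replace each decrease to 120 mg with a decrease by one level according to Table a.
3. In Table 2, for a first grade 3 in a patient already on irinotecan 120 mg/m², reduce regorafenib by one level, as Table 3's 120 mg/m² row does.

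Two matters are for the sponsor's clinicians to decide and are not part of this correction. The first is how grade 3 occurrences are counted across courses. Counting from course 1 has a cost: a patient cut only from 150/160 to 120/160 could be stopped before any regorafenib reduction. The second is whether a repeat grade 3 at 120/120 leads to 80 mg, as the one-level wording would imply, or to discontinuation.

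The cost is a short protocol amendment to a few table entries, with no added patients, visits or analyses.

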ANC < 1500/mm ³	J21*	No dose modification + G-CSF

Protocole NEXT-REGIRI -Version 6.0 du 09/11/2023

Page **44** sur **86**

and Platelets > 100 000/mm ³		
Platelets < 100 000/mm ³	121*	Padusa by 1 dosa laval
Whatever the number of ANC	JZ I"	Reduce by 1 dose level

^{*} or until 28th day as needed (maximum)

Modalities of Reintroduction of treatment : ANC \geq 1500/mm³ and Platelets \geq 100 000/mm³ If the Platelets and/or ANC values are not correct at D28, the patient will discontinue permanently the study treatment.

At the time of Nadir

In the case of a grade 4 neutropenia, whatever the duration or complication i.e by an infection or fever > 38°5, the G-CSF will be administered at the next course of treatment. If the same toxicity continues with G-CSF then the irinotecan dose will be reduced at the dose immediately inferior. If there is a third occurrence of this toxicity, the patient will permanently discontinue the study treatment.

Table 5: Action and dose modification during the administration of Regorafenib in case of hematological toxicity

Hematological toxicity (Modification dose/delay for Regorafenib)			
Grade	Treatment delay	Dose modification	
Grade 0-2	No delay in Regorafenib	No modification dose	
Grade 0-2	treatment	No modification dose	
Grade 3	No delay in Regorafenib	Reduce by 1 dose levelbc	
Grade 3	treatment	heduce by Tuose level	
	Interrupt Regorafenib		
Grade 4	until hematologic	Reduce by 1 dose level ^{bc}	
	toxicity resolves to	heduce by Tuose level	
	Grade ≤ 2ª		

a If no recovery within 30 days, the treatment will be permanently discontinued.

- b If more than 2 dose reductions are necessary, the treatment will be permanently discontinued.
- c Cf table a.

Table 6: Action and dose modification during the administration of Regorafenib in case of non-hematologic toxicity

Non-hematological toxicity (dose modification/delay for Regorafenib) (except hand-foot skin reaction, hypertension, liver function test abnormalities and diarrhea)^a

Grade	Treatment delay	Dose modification
Grade 0-2	No delay in Regorafenib treatment	No dose modification
Grade 3	Interrupt Regorafenib until non hematologic toxicity resolves to Grade ≤ 2 ^b	Reduce by 1 dose level ^{cd}
Grade 4	Discontinue treatment permanently	Discontinue treatment permanently

- a In the absence of nausea/vomiting prophylaxis and diarrhea not treated.
- b If more than 2 dose reductions are necessary, the treatment will be permanently discontinued.

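### Arm A, Table 2: the grade 3 diarrhea rule after course 2 fits only patients raised to irinotecan 150 mg/m², so a patient held at 120/160 is printed 120/160 again

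*Combined protocol and SAP*

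**What the plan says.** Doses are written below as irinotecan (mg/m²) / regorafenib (mg per day). All rules are in protocol section 6.3, arm A, unless stated.

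- **Table 1, after course 1.** Grade 2 diarrhea leads to "Irinotecan at 120 mg/m². Regorafenib at 160 mg per day + prophylactic treatment". Grade 3 leads to "Irinotecan at 120 mg/m² and Regorafenib at 120 mg per day".
- **Table 2, after course 2**, captioned "Action and dose modification during the administration of Irinotecan and Regorafenib after the second course in case of diarrhea". Grade 3 is split by occurrence only. The first occurrence lowers irinotecan to 120 and sets "Regorafenib to 160 mg per day". The second reads "Irinotecan dose is not changed at 120 mg/m² and decrease Regorafenib to 120 mg per day". The third stops treatment. The grade 1 and grade 2 rows also print a fixed regorafenib dose of 160 mg.
- **Table 3, from course 3 on.** Grade 3 is split by the irinotecan dose received (180, 150 or 120). The 150 row begins "1st occurrence: Decrease Irinotecan to 120 mg/m². Regorafenib to 160 mg per day". The 120 row begins "1st occurrence: Irinotecan is not changed at 120 mg/m² and decrease Regorafenib to 120 mg per day", and its second occurrence stops treatment.
- **Table 6**, the general non-hematologic rule for regorafenib, does not apply, because its scope is "except hand-foot skin reaction, hypertension, liver function test abnormalities and diarrhea".

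**The concern.** Table 2 has no entry for a patient who stayed at irinotecan 120 mg/m² in course 2, although Table 1 creates such patients. For them the printed first step after grade 3 diarrhea changes neither drug. Tables 1 to 3 never take irinotecan below 120 mg/m², so regorafenib is the only dose left to cut, and Table 2 does not cut it until a second occurrence.

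At stake is a restart at unchanged doses after diarrhea that worsened from grade 2 to grade 3 over two successive courses, with a risk of further severe diarrhea in course 3. The same event one course earlier or later brings a regorafenib cut, and the protocol gives no reason for the difference. Sites that notice the gap may also resolve it differently.

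**Working it through.** No planned figure is in dispute. The check traces the dose rules and then sizes the problem.

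**1. The state is reachable.** Section 6.1 starts irinotecan at 120 and raises it to 150 at the second infusion only without diarrhea above grade 1 or other toxicity above grade 2. Table 1 sends grade 2 diarrhea in course 1 to 120/160 for course 2.

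**2. First grade 3 diarrhea while on 120/160:**

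| Course of the event | Rule | Next dose | Change |
|---|---|---|---|
| 1 | Table 1, grade 3 | 120/120 | regorafenib 120/160 − 1 = −25% |
| 2 | Table 2, grade 3, first occurrence | 120/160 | none |
| 3 or later | Table 3, 120 row, first occurrence | 120/120 | regorafenib −25% |

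**3. Where Table 2's steps come from.** Its grade 3 sequence is 120/160, then 120/120, then stop. That is the sequence of Table 3's 150 row. Table 3's 120 row is 120/120, then stop, and has no counterpart in Table 2.

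**4. Dose difference in course 3.** Regorafenib is taken on 7 days per course (section 6.1: days 2–8 and 16–22 of the 28-day cycle). As printed: 7 × 160 = 1120 mg. Under the rule of Tables 1 and 3: 7 × 120 = 840 mg. Ratio: 1120/840 = 1.33.

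**5. Patients already lowered to regorafenib 120.** After grade 3 in course 1, Table 1 gives 120/120. If grade 1 or grade 2 diarrhea follows in course 2, Table 2 prints 160 mg, a rise of 160/120 − 1 = 33%. If grade 3 recurs, the printed dose is 160 mg when read as a first occurrence, or the 120 mg already being taken when read as a second. Table 2 does not say whether course 1 episodes count. The same fixed 160 mg would meet a patient whose regorafenib was cut for hematologic toxicity (Table 5) or hand-foot reaction (Table 7).

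**6. How many patients.** The protocol gives neither the share held at 120/160 nor a per-course rate of grade 3 diarrhea. Assumptions: 10% to 25% of the 39 arm A patients are held at 120/160, and 5% to 30% of those have grade 3 diarrhea in course 2.

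- Low: 39 × 0.10 × 0.05 = 0.2 patients.
- High: 39 × 0.25 × 0.30 = 2.9 patients.

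**7. How many could still benefit.** Inclusion is planned from September 2019 to January 2025, 64 months (section 3). This protocol version is dated 9 November 2023, about month 50. With even accrual to plan (an assumption), 39 × 14/64 = 8.5 arm A patients remained.

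- Low: 8.5 × 0.10 × 0.05 = 0.04 patients.
- High: 8.5 × 0.25 × 0.30 = 0.64 patients.

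Time needed to approve an amendment lowers these further.

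**The case against.** The best defense is that Table 2's first grade 3 entry tells the site to decrease irinotecan to 120, which cannot be done for a patient already there. On that view the table is silent about this patient. The next line in the same row and Table 3's 120 row both show the natural step, 120/120. This stands in part. A reader might infer that the protocol deliberately orders an unchanged restart, and the wording does not support that: the entry was plainly written for patients at 150. But the 120/120 line is labeled a second occurrence, Table 3 starts only from course 3, and Table 6 excludes diarrhea. No rule tells the site to cut regorafenib, and the only printed first-occurrence dose is 160 mg.

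Safeguards also count. Irinotecan is held until grade 1 or better, grade 4 stops treatment, section 8.1 lets the investigator stop at any time, and the safety committee reviews the first two months of the first twenty arm A patients (section 10.3). These limit the harm. They do not set the restart dose, and the prophylaxis required after diarrhea above grade 1 was already due in this patient from course 1.

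A reader might also take the 14% of grade 3 or worse diarrhea reported for FOLFIRI plus regorafenib (section 1) as the minimum risk for course 2, and conclude that at least one case is likely. The documents do not support that. The figure is reported for a whole trial rather than one course, the regimen includes 5-FU, and it counts grade 4 events, which stop treatment under Table 2.

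**Conclusion.** The point holds as a drafting gap in arm A dosing safety. For a first grade 3 diarrhea at 120/160, Table 2 prints no cut where Tables 1 and 3 cut regorafenib by 25%, and its fixed 160 mg entries can be read as raising a dose already lowered. The trace of the rules rests on the text alone. The number of patients rests on assumed rates: from well under one to about three of 39, and less than one who could still be helped from the date of this version if accrual went to plan. A reader might infer a threat to the trial's conclusions; nothing in the plan supports that, since the sample size, the primary endpoint and its analysis do not depend on these entries. The gap is worth correcting because the remedy is small and already stands in the protocol's own Table 3.

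**What to change.** Split the grade 3 row of Table 2 by the irinotecan dose received in course 2, as Table 3 does:

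- **Received 150:** the first occurrence gives irinotecan 120 with regorafenib at its current dose; later occurrences stay as now.
- **Received 120 with regorafenib 160:** a first grade 3 in course 2 gives 120/120; the next occurrence stops treatment, as in Table 3's 120 row.
- **Already at 120/120 after grade 3 in course 1:** state whether that episode counts as an occurrence. Whether a further grade 3 should then stop treatment is for the sponsor to decide, since it would be a new stopping rule.

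Throughout Table 2, replace each fixed regorafenib 160 mg entry with *current regorafenib dose (no increase)*.

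The cost is one amendment. Because it touches patient safety it is probably a substantial modification under section 12.6, needing ANSM and/or CPP review. It helps only patients who have not yet reached course 3, and none if all arm A patients have passed that point. Sample size and analysis do not change.
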